SYNOPSIS

| Protocol Title | Contact Lenses with New UV-blocker Manufactured with Different Techniques | |
|-----------------------------------|----------------------------------------------------------------------------------------------------------------------------------------------------------------------------------------------------------------------------------------------------------|--|
| Sponsor | JJVC, [name] | |
| Clinical Phase | Phase 2b | |
| Trial Registration | This study will be registered on ClinicalTrials.gov by the Sponsor. | |
| Test Article(s) | Investigational Products: Senofilcon-based contact lens containing new UV additive - often referred to as Solace. | |
| Wear and Replacement Schedules | Wear Schedule: Daily wear Replacement Schedule: Every two weeks | |
| Objectives | The primary objective of this study is to demonstrate non-inferiority of the Test lens compared to the Control lens with respect to CLUE comfort and quality of vision in order to assess Test lens performance for eventual lock on curing methodology. | |

| Study Endpoints | Primary Endpoint(s): The primary endpoints are overall quality of vision and overall comfort scores using Other observation(s): Other endpoints are being evaluated chiefly to design future studies. 1. Outdoor Performance | |
|-----------------|------------------------------------------------------------------------------------------------------------------------------------------------------------------------------------------------------------------------------------------------------------------------------------------------------------------------------------------------------------------------------------------------------------------------------------------------------------------------------------------------------------------------------------|--|
| Study Design | This study is a randomized, 4-visit, double-masked, 2x3 bilateral crossover, dispensing trial. The study lenses will be worn as daily wear (DW) for a period of two weeks each with one of the study lenses being worn twice. Each study lens is expected to be worn at least five (5) days per week for at least six (6) hours per day worn. There will be no washout period between study lenses. See the flow chart at the end of the synopsis table for the schematic of the study visits and procedures of main observations | |
| Sample Size | Approximately 90 eligible subjects will be enrolled and randomized into the study. Approximately 80 subjects are targeted to complete the study. A replacement subject may be enrolled if a subject discontinues from the study prematurely; the decision whether to enroll replacement subjects will be made by the joint agreement of the Investigator and Sponsor | |

| Study Duration | Subjects will wear the Test and Control lenses for two weeks each in random order with one of the study lenses being worn twice for a total of 6 weeks per subject. The enrollment will be 2 weeks, making the entire study approximately 8 weeks in duration. | |
|---------------------------------|-----------------------------------------------------------------------------------------------------------------------------------------------------------------------------------------------------------------------------------------------------------------------------------------------------------------------------------------------------------------------------------------------------------------------------------------------------------------------------------------------------------------------------------------------------------------------------------------------------------------------------------------------------------------------------------------------------------------------------------------------------------------------------------------------------------------------------------------------------------------------------------------------------------------------------------------------------------------------------------------------------------------------------------------------------------------------------------------------------------------------------------------------------------------------------------------------|--|
| Anticipated Study Population | The subject is a current spherical soft contact lens wearer (defined as a minimum of 6 hours of DW per day, at least 5 days per week, for a minimum of 1 month prior to the study) and willing to wear the study lenses on a similar basis. Subjects must be age 18 and older. | |
| Eligibility Criteria | Eligibility Criteria: | |
| (Inclusion Criteria) | Potential subjects must satisfy all of the following inclusion criteria to be enrolled in the study: | |
| | The subject must read, understand, and sign the STATEMENT OF INFORMED CONSENT and receive a fully executed copy of the form. Appear able and willing to adhere to the instructions set forth in this clinical protocol. Healthy adult males or females age ≥18 years of age with signed informed consent. Eligible presbyopes will be those that wear full distance contact lenses in both eyes, then wear reading glasses over them. The subject is a current spherical soft contact lens wearer (defined as a minimum of 6 hours of DW per day, at least 5 days per week, for a minimum of 1 month prior to the study) and willing to wear the study lenses on a similar basis. Subjects must be able and willing to wear the study lenses at least 6 hours a day, a minimum of 5 days per week. The subject's vertex-corrected spherical equivalent distance refraction must be in the range of -1.00 to -6.00 (inclusive) in each eye. The subject's refractive cylinder must be ≤ -1.00 D in each eye. Have spherocylindrical best corrected visual acuity of 20/25+3 or better in each eye. | |

[figure not shown]
Eligibility Criteria (Exclusion Criteria)

Potential subjects who meet any of the following criteria will be excluded from participating in the study:

- 1. Currently pregnant or lactating.
- 2. Any active or ongoing systemic disease (e.g., Sjögren's Syndrome), allergies, infectious disease (e.g., hepatitis, tuberculosis), contagious immunosuppressive diseases (e.g., HIV), autoimmune disease (e.g. rheumatoid arthritis), or other bodily diseases or infections, by self-report, which are known to interfere with contact lens wear and/or participation in the study.
- 3. Use of systemic medications (e.g., chronic steroid use) that are known to interfere with contact lens wear. Habitual medications taken by successful contact lens wearers are generally considered acceptable.
- 4. Habitual toric, extended wear, or multifocal contact lens wear.
- 5. Any current use of ocular medication.
- 6. Any known hypersensitivity or allergic reaction to Optifree PureMoist.
- 7. Any previous, or planned (during the course of the study) ocular surgery (e.g., radial keratotomy, PRK, LASIK, etc.).
- 8. Participation in any contact lens or lens care product clinical trial within 14 days prior to study enrollment.
- 9. Employee or immediate family member of an employee of clinical site (e.g., Investigator, Coordinator, Technician).
- 10. Any active or ongoing ocular allergies, infections or other ocular abnormalities that are known to interfere with contact lens wear and/or participation in the study. This may include, but not be limited to entropion, ectropion, extrusions, chalazia, recurrent styes, glaucoma, history of recurrent corneal erosions, aphakia, or corneal distortion.
- 11. Any Grade 3 or greater slit lamp findings (e.g., edema, corneal neovascularization, corneal staining, tarsal abnormalities, conjunctival injection) on the FDA slit-lamp scale.
- 12. Binocular vision abnormality or strabismus.
- 13. Any previous history or signs of a contact lens-related corneal inflammatory event (e.g., past peripheral ulcer or round peripheral scar), or any other ocular abnormality that would contraindicate contact lens wear.

| Disallowed Medications/Interventions | Use of any prescription or over-the-counter (OTC) medications that may affect contact lens wear from 24 hours prior to receiving the study product through the study period of ~ 6 weeks. Habitual medications taken by successful soft contact lens wearers are considered acceptable. Note that habitual medications should be taken throughout the study period. |
|------------------------------------------------------------------|----------------------------------------------------------------------------------------------------------------------------------------------------------------------------------------------------------------------------------------------------------------------------------------------------------------------------------------------------------------------------------------------------------------------------------------------------|
| Measurements and Procedures | Subjective assessments, physiological responses, fitting characteristics. |
| Microbiology or Other Laboratory Testing | None |
| Study Termination | The occurrence of one or more Unanticipated Adverse Device Effect (UADE), or any SAE where relationship to study agent cannot be ruled out, will result in stopping further dispensing investigational product for further investigation. In the event of a UADE or SAE, the Sponsor Medical Monitor may unmask the treatment regimen of subject(s) and may discuss this with the Principal Investigator before any further subjects are enrolled. |
| Ancillary Supplies/ Study- Specific Materials | Opti-Free® PureMoist®, Preservative-free rewetting drops/artificial tears |
| Principal Investigator(s) and Study Institution(s)/Site(s) | A full list of Principal Investigators, clinical sites, and institutions is kept separately from the Study Protocol and is included in the study Trial Master File. |

Figure 1: Study Flowchart

COMMONLY USED ABBREVIATIONS AND DEFINITIONS OF TERMS

ADD Plus Power Required for Near Use

ADE Adverse Device Effect

AE Adverse Event/Adverse Experience
BCVA Best Corrected Visual Acuity

BSCVA Best Spectacle Corrected Visual Acuity

CFR Code of Federal Regulations
CLUE Contact Lens User Experience

COAS Complete Ophthalmic Analysis System

COM Clinical Operations Manager CRA Clinical Research Associate

CRF Case Report Form

CRO Contract Research Organization

CT Center Thickness

CTP Clinical Technical Procedure

D Diopter

DMC Data Monitoring Committee eCRF Electronic Case Report Form EDC Electronic Data Capture

ETDRS Early Treatment Diabetic Retinopathy Study

FDA Food and Drug Administration

GCP Good Clinical Practice

HIPAA Health Insurance Portability and Accountability Act

IB Investigator's Brochure ICF Informed Consent Form

ICH International Conference on Harmonization

IDE Investigational Device Exemption
IEC Independent Ethics Committee
IRB Institutional Review Board

ISO International Organization for Standardization

ITT Intent-to-Treat

JJVC Johnson & Johnson Vision Care, Inc.

LC Limbus Center

LogMAR Logarithm of Minimal Angle of Resolution
MedDRA[©] Medical Dictionary for Regulatory Activities

MOP Manual of Procedures

NIH National Institutes of Health

OD Right Eye

OHRP Office for Human Research Protections
OHSR Office for Human Subjects Research

OS Left Eye
OU Both Eyes

PD Protocol Deviation

PHI Protected Health Information

PI Principal Investigator
PIG Patient Instruction Guide

| PQC | Product Quality Complaint |
|-----|----------------------------------|
| PRO | Patient Reported Outcome |

OA Quality Assurance OC **Quality Control**

SAE Serious Adverse Event/Serious Adverse Experience

Statistical Analysis Plan SAP Statistical Analysis System SAS

SD Standard Deviation

SOP Standard Operating Procedure

UADE Unanticipated Adverse Device Effect

Unanticipated Serious Adverse Device Effect **USADE**

VA Visual Acuity

INTRODUCTION AND BACKGROUND

Curing is the process used in manufacturing of contact lenses that solidifies the monomer into a lens shape. Curing is achieved at JJVC by the use of special lights assembled in a light tunnel within the manufacturing line. Historically, the lights have varied in intensity throughout the tunnel. It is unknown what happens if the manufacturing line stalls and the lens is exposed to a static curing process. A static curing process is also a more robust process and is therefore desirable provided similar clinical performance to a variable intensity process.

The present study is designed to demonstrate non-inferiority of the Test lens (static-curing process) compared to the Control lens (step-curing process) with respect to and quality of vision.

1.1. Name and Descriptions of Investigational Products

This study will evaluate two senofilcon-based contact lenses containing a new UV-blocker. Both lenses are investigational. they will serve as the Control lens while the lenses manufactured with static-curing will serve as the Test lens.

1.2. Intended Use of Investigational Products

The intended use of the investigative product in this study is for correcting myopia and providing visual benefits in bright lighting situations. During the study, each test article will be worn bilaterally in a daily wear modality for at least 6 hours per day and 5 days per week for approximately two weeks each. The subject will wear either the test or control article twice and the other study article once.

1.3. Summary of Findings from Nonclinical Studies

[figure not shown]
All previous pre-clinical findings were deemed satisfactory prior to proceeding with clinical trials on humans. For the most comprehensive nonclinical information regarding senofilcon A with new UV-blocker, refer to the latest version of the Investigator's Brochure.

1.4. Summary of Known Risks and Benefits to Human Subjects

The risks of wearing soft contact lenses are well known and are described in the Investigator's Brochure and Informed Consent. The material safety testing/lens release criteria was determined based on the Risk Assessment. Benefits to the subjects include the correction of their refractive error with the potential of improved 'visual comfort' in bright lighting environments.

For the most comprehensive risk and benefit information regarding senofilcon A with new UV-blocker, refer to the latest version of the Investigator's Brochure.

2. STUDY OBJECTIVES, ENDPOINTS AND HYPOTHESES

2.1. Objectives

Primary Objective(s)

The primary objective of this study is to compare the clinical performance of two study contact lenses using different curing techniques with respect to CLUE comfort and vision.

Other Objectives(s)

Other objectives of this study are to compare the clinical performance of two study contact lenses using different curing techniques with respect to driving, indoor and outdoor performance items, CLUE handling and the rate of Grade 3 or higher slit lamp findings.

2.2. Endpoints

Primary Endpoint(s)

CLUE Comfort and Vision

The primary endpoints are overall quality of vision and overall comfort scores using Contact Lens User Experience (CLUE)TM questionnaire at the two-week follow-up. CLUE is a validated patient-reported outcomes questionnaire to assess patient-experience attributes of soft, disposable contact lenses (comfort, vision, handling, and packaging) in a contact-lens wearing population in the US, ages 18-65. Scores follow a normal distribution with a population average score of 60 (SD 20), where higher scores indicate a more favorable/positive response.

Other Observation(s)

Other endpoints are being evaluated chiefly to design future studies.

1. Driving Performance

Driving performance will be assessed by two individual patient reported outcome (PRO) questions at the 2-week follow-up evaluation. The individual items are as follows:

- A. Reduction in glare while driving during the day (Item ID: MIS00617)
- B. Reduction in glare while driving during the night (Item ID: MIS00618)

2. Indoor Performance

Indoor performance will be assessed by three individual patient reported outcome (PRO) questions at the 2-week follow-up evaluation. The individual items are as follows:

- A. Reduction in glare from the computer screen (Item ID: MIS00628)
- B. Reduction in glare caused by bright indoor lights (Item ID: MIS00625)
- C. Reduction in glare caused by bright light coming through the window (Item ID: MIS00626)

3. Outdoor Performance

Outdoor performance will be assessed by four individual patient reported outcome (PRO) questions at the 2-week follow-up evaluation. The individual items are as follows:

- A. Ability to see comfortably in bright sunlight (Item ID: MIS00613)
- B. Reduction in glare in bright sunlight (Item ID: MIS00614)
- C. Reduction in squinting in bright sunlight (Item ID: MIS00615)
- D. Reduction in eye strain in bright sunlight (Item ID: MIS00616)

All driving, indoor and outdoor (PRO) items above will be assessed using the same excellence scale of; 0: Not Applicable, 1: Excellent, 2: Very Good, 3: Good, 4: Fair and 5: Poor.

4. CLUE Handling

Handling scores will be assessed by using Contact Lens User Experience (CLUE)TM questionnaire at the two-week follow-up.

5. Physiological Response assessed at each visit.

2.3. Hypotheses

Primary Hypotheses

| Primary Hypotheses | | |
|----------------------|------------------------------------------------------------------------------------------------------------------------------------------------------------------------------------|--|
| Endpoint | Hypothesis | |
| Overall CLUE Vision | The test lens will be non-inferior to the control lens at the 2-week follow-up with respect to CLUE overall quality of vision. A non-inferiority margin of -5 points will be used. | |
| Overall CLUE Comfort | The test lens will be non-inferior to the control lens at the 2-week follow-up with respect to CLUE overall comfort. A non-inferiority margin of -5 points will be used. | |

Both Primary hypotheses must be met for this study to be considered successful.

Other Hypotheses

| | Other Hypotheses | | | |
|---------------------------------|-------------------------------------------------------------------------------------------------------------------------------------------------------------------------------------------------------------------------------------------------------------------------------------------------------------------------------------------------------------------------------------------------------------------------|--|--|--|
| Endpoint | Hypothesis | | | |
| Outdoor Performance Measures | The test lens will be superior to the control lens in at least 2 of the following 4 outdoor performance measure(s) at the 2-week follow-up. An odds ratio margin of 1 will be used. 1. Ability to see comfortably in bright sunlight 2. Reduction in glare in bright sunlight 3. Reduction in squinting in bright sunlight 4. Reduction in eye strain in bright sunlight | | | |
| Driving Performance Metrics | The test lens will be non-inferior to the control lens in both of the following driving performance metrics at the 2-week follow-up. An odds ratio margin of 0.67 will be used. 1. Reduction in glare while driving during the day 2. Reduction in glare while driving during the night | | | |
| Indoor Performance Measures | The test lens will be superior to the control lens in at least 2 of the following 4 outdoor performance measure(s) at the 2-week follow-up. An odds ratio margin of 1 will be used. 1. Reduction in squinting while working on the computer 2. Reduction in glare from the computer screen 3. Reduction in glare caused by bright indoor lights 4. Reduction in glare caused by bright light coming through the window | | | |
| CLUE Handling | CLUE handling of the step-cure and static cure lenses will be no different from each other. | | | |
| Physiological Response | Physiological responses of the step-cure and static cure lenses will be no different from each other. | | | |

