5.2. Masking

Both test lenses will contain the same new UV-blocker. Therefore, double-masking is possible and will be used to keep both the subject and investigators masked to the identity of the study lenses throughout the duration of the study period. Every attempt will be made to keep the other clinical trial personnel involved in the study (e.g. Data management and Biostatistician) unaware of the identity of the study lenses.

The identity of the study lenses will be masked by over labeling the blister packs with a label containing the study number, lot number, sphere power, expiration date and the randomization codes P or W. Only the personnel involved in the over labeling and the unmasked statistician will have access to the lens decode information translating the randomization codes into test and control groups. The medical monitor will also have access to the decode information in case breaking the mask is necessary for the urgent medical treatment of a subject.

Masking will be used to reduce potential bias. Subjects will be unaware of the identity of the investigational product. Investigators and clinical site personnel involved in the data collection will be masked as to the identity of the investigational product.

Under normal circumstances, the mask should not be broken until all subjects have completed the study and the database is finalized. Otherwise, the mask should be broken only if specific emergency treatment/course of action would be dictated by knowing the treatment status of the subject. In such cases, the Investigator may, in an emergency, contact the medical monitor. In the event the mask is broken, the Sponsor must be informed as soon as possible. The date, time, and reason for the unmasking must be documented in the subject record. The Investigator is also advised not to reveal the study treatment assignment to the clinical site or Sponsor personnel.

Subjects who have had their treatment assignment unmasked are expected to return for all remaining scheduled evaluations. Subjects who are discontinued will be replaced.

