14.2. Sample Size Justification

This study was designed and powered to show non-inferiority between the Test lens compared to the Control lens with respect to CLUE comfort and vision. It was assumed there was no difference between the Test and Control lenses. The sample size was calculated to achieve a minimum statistical power of 90% and a type I error of 5%.

The sample size calculation was based on historical data from a similar study, CR-5960 The Test lens from CR-5960 is the Control for this study. CR-5960 enrolled 133 subjects, of which 130 (97.7%) were dispensed study lenses. Of the dispensed subjects, 127 (95.5%) completed the study and 3 (2.3%) subjects were discontinued. The per-protocol population included 121 (91.0%) subjects out of the total 127 that completed. Table 4 summarizes CLUE scores from CR-5960 at the 2-week follow-up.¹³

Table 4: Descriptive CLUE scores from CR-5960 (Historical Data)

| CLUE Domain | Study Lenses | |
|-----------------------------------|------------------|---------------------------|
| | Acuvue Oasys | Solace – 25% differential |
| Comfort [mean (SD ¹)] | 61.185 (24.2024) | 64.339 (24.2132) |
| Vision [mean (SD ¹)] | 66.792 (20.0073) | 69.445 (20.1752) |

¹SD: Standard Deviation

Sample size calculation for CLUE comfort and vision were carried out using an approximation of the power of an F-test derived from the non-centrality parameter calculated form the observed F-statistic of a linear model. ¹⁴

Model details:

CLUE comfort and vision were analyzed separately using a linear mixed model. Lens type, was included as the only fixed effect. A compound symmetric (CS) covariance was used to model the correlation between measurements within the same subject across study periods. Below is the variance-covariance matrix used in the CLUE each model.

$$\sum_{comfort} \begin{pmatrix} 349.3 & 110.9 & 110.9 \\ 110.9 & 349.3 & 110.9 \\ 110.9 & 110.9 & 349.3 \end{pmatrix}$$

$$\sum_{vision} \begin{pmatrix} 257.4 & 82.1 & 82.1 \\ 82.1 & 257.4 & 82.1 \\ 82.1 & 82.1 & 257.4 \end{pmatrix}$$

Table 5: Sample Size Calculations for CLUE Comfort and Vision

| CLUE Domain | Number to Complete | Power (%) |
|--------------------|--------------------|-----------|
| Comfort | 50 | 77% |
| | 60 | 85% |
| | 80 | 93% |
| Vision | 50 | 88% |
| | 60 | 93% |
| | 80 | 98% |

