14.7. Other Exploratory Analyses

Driving, Indoor and Outdoor Performance

Each driving, indoor and outdoor performance item will be analyzed separately using a generalized linear mixed model for ordinal data with a multinomial distribution and cumulative logit as a link function. The experimental design factors: sequence of lens wear, period, lens type, first order carryover effect will be included in each model as fixed effects. Site will be included as a random effect. An appropriate covariance structure will be used to model the residual errors between measurements within same subject across study periods.

The assumption of proportionality of odds across response categories will be assessed graphically. If this assumption is violated then the distribution of responses will be investigated. If sparse data is observed then the sparse response categories may be collapsed to ensure there is sufficient data for analysis. If the assumption of proportionality of odds is still violated in the collapsed categories then a partial proportional odds model may be considered. If any of the above models fail to converge, then reduced versions may be considered. A Generalized Estimating Equation (GEE) may also be considered as necessary.

Comparison between the test lens and the control lens at the 2-week follow-up will be carried out using two-sided 95% confidence intervals of the odds ratios (Test over Control); where the odds ratio represents the odds of having a higher positive rating/experience for the Test lens compared to the Control lens.

For driving items, non-inferiority of the test lens relative to the control will be concluded if the lower limit of the 95% confidence interval of the odds ratio is above 0.67. If non-inferiority is met, then superiority will be tested. Superiority of the test lens relative to the control lens will be concluded if the lower limit of the confidence interval of the odds ratio is above 1.

CLUE Handling

CLUE handling will be analyzed and tested in the same exact manner as CLUE comfort and vision as describe above in Section 14.5.

Physiological Responses will be descriptively summarized for each lens type.

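### The exploratory outdoor and indoor hypotheses ask for superiority, although the visible design points to keeping performance; non-inferiority at the driving margin would fit better

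*Combined protocol and SAP*

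**What the plan says.** All references are to the combined protocol and SAP.

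- **Section 2.3, outdoor row:** "The test lens will be superior to the control lens in at least 2 of the following 4 outdoor performance measure(s", and "An odds ratio margin of 1 will be used".
- **Section 2.3, indoor row:** the same sentence, including the word outdoor, and the same margin. It lists four items, the first being "Reduction in squinting while working on the computer". Section 2.2 lists three indoor items and this is not one of them.
- **Section 2.3, driving row:** non-inferiority on both glare items. "An odds ratio margin of 0.67 will be used".
- **Section 5.2:** "Both test lenses will contain the same new UV-blocker". In Table 1 (Section 6.1) the legible rows agree for the two lenses except for cure technique.
- **Introduction and Background:** a static process "is therefore desirable provided similar clinical performance to a variable intensity process".
- **Section 14.2:** "It was assumed there was no difference between the Test and Control lenses". The sentence just before it ties the sizing to CLUE comfort and vision.
- **Section 14.7:** two-sided 95% intervals for the odds ratio are planned for every driving, indoor and outdoor item. The decision rule that follows is for one group only: "For driving items, non-inferiority of the test lens relative to the control will be concluded if the lower limit" of the 95% interval exceeds 0.67, with superiority as a second step if it exceeds 1.
- **Status:** Section 2.2 presents these endpoints as mainly serving the design of later studies. Section 2.3 rests study success on the two CLUE hypotheses alone.

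**The concern.** The study is meant to inform the choice of curing method (Synopsis), and the intended use includes a visual benefit in bright light (Section 1.2). For that choice, the natural question about the outdoor and indoor items is whether static curing loses any of the benefit. The rest of the visible plan is framed in that way: non-inferiority for comfort, vision and driving glare, and no expected difference for handling and physiology.

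The outdoor and indoor rows instead require the static-cure lens to beat the step-cure lens. If the lenses perform alike, both hypotheses will nearly always be recorded as not met, and nothing pre-specified would let the sponsor say that performance was kept. Comparing these items' intervals with 0.67 after the fact would be post hoc.

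**Working it through.** **1. The plan's own figure.** There is none for these items. Table 5 gives power for CLUE comfort and vision only, and no effect size, response distribution or correlation is stated for any outdoor or indoor item.

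**2. Chance of meeting the superiority rule if the odds ratio is 1.** A two-sided 95% interval (Section 14.7) leaves 0.025 in the favourable tail for each item, whatever the sample size. For four independent items:

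P(2 or more) = 1 − 0.975⁴ − 4 × 0.025 × 0.975³ = 1 − 0.90369 − 0.09269 = 0.0036.

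For the three indoor items of Section 2.2: 1 − 0.975³ − 3 × 0.025 × 0.975² = 0.0018.

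For correlated items, 2,000,000 draws of equicorrelated normal statistics, each compared with 1.96, give:

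| Correlation between item statistics | 2 of 4 | 2 of 3 |
|---|---|---|
| 0 | 0.36% | 0.18% |
| 0.3 | 1.1% | 0.6% |
| 0.5 | 1.7% | 1.1% |
| 0.7 | 2.3% | 1.6% |
| 0.9 | 2.7% | 2.2% |
| 1 | 2.5% | 2.5% |

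At an odds ratio of 1, each four-item hypothesis therefore fails with probability 97.3% to 99.6%. More subjects would not change this.

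**3. Standard error of the log odds ratio (assumption-based).** There are 80 completers × 3 periods = 240 observations. With Test/Control/Control and Control/Test/Test in equal numbers, 120 are on each lens. The proportional-odds information is V = 120 × 120 × 240 / (3 × 241²) × (1 − Σp³) = 19.83 × (1 − Σp³), where p are the category proportions. The design, adjusted for sequence, period and carryover, multiplies the variance by (9/8)(1 − ρ), where ρ is the within-subject correlation.

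For five equally used categories, Σp³ = 5 × 0.2³ = 0.04 and V = 19.04. At ρ = 0, SE = √(1.125 / 19.04) = 0.243. A strongly skewed distribution gave 0.254.

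**4. Per-item power for non-inferiority at 0.67, true odds ratio 1.** Power = Φ(0.400 / SE − 1.96), since −ln 0.67 = 0.400.

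| ρ | SE, uniform to strongly skewed | Power |
|---|---|---|
| 0 | 0.243 to 0.254 | 38% to 35% |
| 0.3 | 0.203 to 0.213 | 50% to 47% |
| 0.5 | 0.172 to 0.180 | 64% to 61% |
| 0.7 | 0.133 to 0.139 | 85% to 82% |

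Under the superiority rule the corresponding figure is 2.5% throughout.

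**5. If every item must pass.** For four independent items, power runs from 0.35⁴ = 1.5% to 0.85⁴ = 52%. If the items are fully correlated it equals the per-item 35% to 85%.

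**6. If there is a real benefit.** Per-item superiority power, Φ(ln OR / SE − 1.96), over the same range of SE (0.254 to 0.133) is about 36% to 86% at an odds ratio of 1.5 and 78% to 99.9% at 2.0.

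**The case against.** The strongest reply is that no section assumes an odds ratio of 1 for these items. Section 14.2 makes its assumption while sizing CLUE comfort and vision. A reader might infer that the study as a whole assumes no difference and that these hypotheses are bound to fail. The documents do not support that: the figure of 0.4% to 2.7% is conditional, and step 6 shows that a real benefit could well be detected. This stands, and it limits the point.

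Three further readings also go too far:

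- **That the objective fails.** Section 2.1 sets out only to compare the lenses on these items, and reporting the odds ratios and intervals meets that. Only the hypotheses in Section 2.3 can fail.
- **That a worse lens would look the same as an equal one.** That is true of the failed superiority test alone. The planned two-sided intervals would shift for a materially worse lens, and driving glare already has a non-inferiority test. What is missing is a pre-specified rule, not the information.
- **That there is no rationale for superiority.** The Introduction and Section 1.1 have gaps in the text, and Table 1 has a blank row. The Introduction says that the effect of static exposure when the line stalls is unknown, and Section 7.4 measures light transmission of worn Test lenses. The visible text gives no reason to expect less glare with static curing, but one may have been removed.

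The endpoints are also exploratory and outside the success rule. That lowers the stakes but does not explain why driving glare is tested for non-inferiority while sunlight, screen and indoor-light items are tested for superiority.

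**Conclusion.** The point holds as a mismatch between hypothesis and purpose in two exploratory families. If the no-difference assumption extends to these items, which is an inference supported by the Introduction, Section 5.2 and Table 1, each four-item hypothesis is met about 0.4% to 2.7% of the time and any pass is a false positive. A failed test would not by itself show that bright-light performance is kept.

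That range rests on an odds ratio of 1 and equicorrelated normal statistics; it does not depend on sample size. The power figures for the alternative rest on assumed response distributions and within-subject correlations of 0 to 0.7. Study success is unaffected, so this is a worthwhile and cheap improvement rather than a flaw in the primary comparison. The wrong word and the extra item in the indoor row are plain inconsistencies that hold without any assumption.

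**What to change.** 1. In Section 2.3, restate the outdoor and indoor hypotheses as non-inferiority of Test to Control, using the 0.67 odds ratio margin already set for driving, with a sentence on why that margin suits these items.
2. In Section 14.7, extend the driving rule to them: lower 95% limit above 0.67, then superiority if it is above 1. A real advantage could still be claimed.
3. State how many items must pass. Two of four is too lenient for non-inferiority, because retention could be declared with the other two items worse. The driving row requires both of its items; requiring all items here would be consistent and needs no multiplicity adjustment.
4. Correct the indoor row: replace the word outdoor, and reconcile its four items with the three in Section 2.2, either by adding the computer-squinting item there or by removing it here.
5. If the sponsor does expect superiority, keep it, state the rationale and the expected odds ratio, and add the missing decision rule to Section 14.7.

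The cost is wording only: no new data, visits or subjects. The downside is a weaker claim than superiority and only moderate power, roughly 35% to 85% per item at an odds ratio of 1. It will be lower if all items must pass, or if many subjects choose the not-applicable response, which reduces the 240 observations.
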